- If AE onset date \leq date of End of Treatment visit in the preceding trial (1407-0030) < AE worsening date < date of first intake after week 12 re-assignment, then the AE is assigned to “first 12 weeks of treatment”.

If an AE worsening occurs on the day of week 12 visit, actual time between AE onset and study medication taken will be compared to determine AE time period (first 12 weeks, second treatment period).

If the subject discontinues before the day of week 12 visit, date of first intake after week 12 re-assignment will be missing, the AE worsening will still be assigned to “first 12 weeks of treatment”.

- If date of first intake after week 12 re-assignment \leq AE worsening date \leq date of last intake + 7 days, then the AE is assigned to “second treatment period”.

For patients who rolled over from Part 1 of the 1407-0030 trial if the onset date of an AE occurs prior to Week 12 and continues beyond Week 12 with a worsening RCTC grade after Week 12 then the AE will be captured as a TEAE both during the first 12-week period of 1407-0005 (as a new-onset TEAE) and during the second treatment period (beyond Week 12, as a worsening-TEAE).

Because there is no scheduled titration for patients who rolled over from Part 2 of trial 1407-0030 adverse events will only be summarized for the entire treatment period and will not be summarized for the first 12 weeks and after 12 weeks for these patients.

Due to differing doses, differing titration schedules and different timeframe for entering this study between patients from part 1 and part 2 of trial 1407_00030, several sets of adverse event analyses, each consisting of 11 summaries, will be presented:

- Events up to 12 weeks for patients who rolled over from Part 1 of trial 1407_00030 with treatment columns BI 25 mg, BI 50 mg, BI 100 mg and BI 200 mg
- Events after 12 weeks for patients who rolled over from Part 1 of trial 1407_00030

with treatment columns BI 25 mg/BI 100 mg, BI 50 mg/BI 100 mg, BI 100 mg/BI 100 mg and BI 200 mg/ BI 200mg.

- All events for patients who rolled over from Part 2 of trial 1407-0030 with treatment column BI 400 mg
- All events from all patients who rolled over from trial 1407-0030 (part 1 and part 2 combined) where events are classified under the treatment at onset in 1407-0005 with treatment columns BI 25 mg, BI 50 mg, BI 100 mg, BI 200 mg and BI 400 mg

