Patients from part 1 of trial 1407_00030 who discontinue study treatment prior to Week 12 will be excluded from the second and fourth sets of analyses above. Due to varying length of exposure to the various doses, exposure adjusted incidence rates will be presented in addition to number and percentage of patients with events in the fifth set above (classification by dose at onset).

For the analysis of other safety data (laboratory data, vital signs ,suicidal ideation) summaries will be presented for the entire study, for the first 12 weeks of the study and after 12 weeks on study. For these outputs data from patients who rolled over from Part 1 and Part 2 of study 1407-0030 will be combined. In some of these data displays each treatment appears on a separate page. If deemed appropriate, additional displays showing descriptive statistics with figures for selected outcomes will be presented.

For efficacy summaries of response at Week 24 all patients from Part 1 of trial 1407-0030 will have data will be grouped as follows:

- 100 mg patients from part 1 of trial 1407-0030
 - 25 mg/100mg
 - 50 mg/100 mg
 - 100 mg/100mg
- 200 mg patients from part 1 of trial 1407-0030
- All patients from part 1 of trial 1407-0030
- 400 mg patients from part 2 of trial 1407-0030
- All patients from part 1 and part 2 of trial 1407-0030 combined

For efficacy summaries of time to loss of response data will be grouped as follows:

- 100 mg patients from part 1 of trial 1407-0030 (combing 25 mg/100mg, 50 mg/100 mg and 100 mg/100mg)
- 200 mg patients from part 1 of trial 1407-0030
- 400 mg patients from part 2 of trial 1407-0030

Efficacy response at Week 12 and 36 for patients from Part 2 of trial 1407-0030 will be summarized.

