7.4 PRIMARY ENDPOINT(S)

7.4.1 Primary analysis of the primary endpoint(s)

The primary endpoint is the occurrence of treatment emergent adverse events (TEAEs) up to Week 288. The primary analysis will be based on the exposure adjusted rate of patients reporting a treatment emergent adverse event (TEAE) up to Week 288.

Exposure-adjusted adverse event incidence rates will be calculated using the following approach:

- The incidence rate (per 100 subject years) of a selected adverse event (also known as the incidence density rate or person-time incidence rate) is defined as the number of subjects experiencing the adverse event per treatment group during the time at risk divided by the total time of subjects at risk in that treatment group to contribute an event to the analysis multiplied by 100 (per 100 subject years), where for each subject and each TEAE preferred term:

$$\text{Time at risk [subject years]} = (\text{date of first onset of AE} - \text{study drug start date} + 1) / 365.25$$

If, for a subject, no treatment emergent adverse event occurred for the preferred term, then the time at risk will be censored at the minimum of (date of death; drug stop date + 7 days; last contact date).

- For each AE, the incidence rate will therefore be calculated as:

$$\text{Incidence rate [per 100 subject years (pt-yrs)]} = 100 * \text{number of subjects with TEAE} / \text{Total TEAE-specific time at risk [subject years].}$$

Exact 95% confidence intervals (CI) around the observed AE incidence rate will also be provided using exact Poisson regression.

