7.8.1 Adverse Events

The analyses of adverse events will be descriptive in nature. All analyses of AEs will be based on the number of patients with AEs (not the number of AEs).

Unless otherwise specified, the analyses of AEs will be descriptive in nature. All analyses of AEs will be based on the number of subjects with AEs and NOT on the number of AEs.

The analysis of AEs will be based on the concept of treatment emergent AEs. That means that all AEs occurring between first drug intake till 7 days after last drug intake will be assigned to the received treatment. All AEs occurring before first drug intake will be assigned to 'screening' and all AEs occurring after last drug intake + 7 days will be assigned to 'follow-up' (for listings only). For details on the treatment definition, see [Section 6.1](#).

According to ICH E3 [\(5\)](#), in addition to Deaths and serious adverse events, 'other significant' AEs need to be listed in the clinical trial report. These will be any non-serious adverse event that led to an action taken with study drug (e.g. discontinuation or dose reduced or interrupted). An overall summary of adverse events will be presented.

The frequency of subjects with AEs will be summarised by treatment, primary system organ class and PT using the version of MedDRA at the database lock. Separate tables will be provided for subjects with SAEs, AEs leading to treatment discontinuation and related AEs.

The system organ classes will be sorted by default by decreasing frequency and PTs will be sorted by decreasing frequency within SOC.

For further details on summarization of AE data, please refer to the guideline 'Handling and summarization of adverse event data for clinical trial reports and integrated summaries' [\(4\)](#).

The severity of AEs will be summarised by the maximum intensity of the events each patient had (as indicated by the recorded RCTC version 2 grade). This will show the number and percent of patients who had at most mild, moderate, severe, and life threatening events. Severe adverse event is defined as an AE with RCTC grade equals to 3 (severe) or 4 (life threatening).

Groupings of adverse events and adverse events of special interest (AESI)

The AESI have been defined in the protocol.

Other user-defined special adverse event grouped term for BI 730357 specified in the following [Table 7.8.1:1](#).

Table 7.8.1: 1 User Defined Adverse Event Group Terms

N	Term	Definition #

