1	SMQ Drug Related Hepatic Disorders	SMQ Drug related hepatic disorders – comprehensive search (20000006)
2	SMQ Opportunistic infections	MedDRA SMQ Opportunistic Infections (narrow)
3	Tuberculosis related terms	BIcMQ “Tuberculosis related terms” BIcMQ (30000107)(broad)
4	Severe infections	SOC “Infections and infestations” with eCRF severity grade >= Rheumatology Common Toxicity Criteria (RCTC) Grade 3
5	Gastritis related terms	
 BIcMQ Gastritis (broad) [32008061]

This column indicates whether the Term(s) provided in the second column are MedDRA preferred terms (PT), Standardised MedDRA Queries (SMQ) or BI customised MedDRA Queries (BIcMQ).

In addition, adjudicated MACE (provided by [REDACTED] will be summarized by indication, treatment, primary system organ class and preferred term.

The user defined AE categories will be updated accordingly with Safety SAP updates.

The following periods will be defined for assessing adverse events for patients from Part 1 of the 1407-0030 trial.:

- First 12 weeks of treatment
- Second treatment period

For patients from Part 1 of the 1407-0030 trial, AEs with onset date on day of week 12 visit, the AE onset time will be compared with first drug administration time of the dose dispensed at the Week 12 visit to determine AE period. The treatment label for second period will be a combination of actual treatment in first 12 weeks of treatment and second period treatment.

Additionally an analysis including patients from both parts of the 1407-0030 trial will be performed in which adverse events are classified under the dose the patient was receiving at the onset of the TEAE.

AE summaries

An overall summary of adverse events will be presented. The frequency of patients with adverse events will be summarized by treatment, primary system organ class and preferred term according to MedDRA. Separate tables will be provided for patients with:

- Drug-related AEs
- AESIs

- AEs leading to discontinuation
- Serious AEs
- Other significant AEs
- AE by worst RCTC intensity
- Investigator defined drug-related serious AEs
- User defined AE categories

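### The Part 1 after-Week-12 adverse event set compares dose sequences by number and percentage only; SAP 6.1 should add exposure-adjusted rates by sequence

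*SAP*

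**What the plan says.** SAP 6.1 lists four sets of adverse event summaries: Part 1 up to Week 12, Part 1 after Week 12, all Part 2 events, and all patients classified by dose at onset. The second is described as "Events after 12 weeks for patients who rolled over from Part 1 of trial 1407_00030". Its columns are the dose sequences 25/100, 50/100, 100/100 and 200/200 mg. SAP 7.8.1 confirms the labelling: "The treatment label for second period will be a combination of actual treatment in first 12 weeks of treatment and second period treatment". SAP 6.1 presents the split of Part 1 events by period as part of the main safety analyses, whereas SAP 7.8.1 introduces the dose-at-onset classification as an additional analysis.

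On the measure, SAP 6.1 gives a reason, "Due to varying length of exposure to the various doses", and then says that "exposure adjusted incidence rates will be presented in addition to number and percentage of patients with events in the fifth set above". A bracket identifies that set as the one classified by dose at onset, which is the fourth listed. No rate is mentioned for the after-Week-12 set. SAP 7.8.1 describes the tables as frequencies of patients: "All analyses of AEs will be based on the number of subjects with AEs and NOT on the number of AEs".

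SAP 7.4.1 says: "The primary analysis will be based on the exposure adjusted rate of patients reporting a treatment emergent adverse event (TEAE) up to Week 288". It defines the rate per treatment group and counts time at risk from the study drug start date. It does not say which sets or columns it covers, and it does not split at Week 12.

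**The concern.** The reason that SAP 6.1 gives for adjusting one set applies equally to the after-Week-12 set. Part 1 patients "who discontinue study treatment prior to Week 12 will be excluded from the second and fourth sets of analyses above", so everyone in the second set reached Week 12, but each patient's period then ends 7 days after the last intake. One patient may contribute a few days and another more than five years. The protocol's flow chart footnotes add a further source of unequal follow-up, because the timing of the end-of-treatment visit depends on approval in each country.

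A percentage of patients with an event rises with time on drug. If patients in one sequence stay longer than in another, their column shows more patients with events even when the hazard is the same. The reverse can also happen: a sequence with a higher hazard but shorter stay can look safer. This table shows long-term Part 1 safety by the dose a patient came from, in a trial whose stated aim is long-term safety information.

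**Working it through.** **1. The plan's own figures.** Week 288 is 288 × 7 = Day 2016, which matches SAP Table 6.7: 1. Visit 2 / Week 12 is Day 84. The planned after-Week-12 period is 2016 − 84 = 1932 days = 276 weeks, and 1932 / 365.25 = 5.29 years. The minimum is a single dose plus the 7-day residual effect period.

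**2. Does another analysis supply the missing rate?**
- SAP 7.4.1 counts from study drug start. Applied to events after Week 12, that clock adds 84 / 365.25 = 0.23 years per patient in which no such event could be counted, and this weighs more on patients who leave early.
- The dose-at-onset set puts 25/100, 50/100 and 100/100 mg patients into one 100 mg column while they take 100 mg. Its 100 mg column includes the first 12 weeks of the 100/100 mg patients, and its 200 mg column those of the 200/200 mg patients. It yields rates for 100 mg and 200 mg, but none for a sequence after Week 12.
- SAP 7.7 reports extent of exposure by actual treatment, not by sequence. It shows that durations differ but does not adjust for them.

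**3. Size under stated assumptions.** The documents give neither drop-out nor event rates by sequence, so everything below is an assumption. Take a constant event hazard L (the same in both columns), a constant drop-out hazard m and T = 5.29 years.

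- Crude proportion = L/(L+m) × (1 − exp(−(L+m)T))
- Expected time at risk = (1 − exp(−(L+m)T))/(L+m)
- Rate = crude proportion / time at risk = L, whatever m is

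With m = 0.2 and 0.6 per year, mean time on drug, (1 − exp(−mT))/m, is 3.26 and 1.60 years.

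| Events per 100 patient-years | Crude %, m = 0.2 | Crude %, m = 0.6 | Apparent ratio | True ratio |
|---|---|---|---|---|
| 2 | 6.3 | 3.1 | 2.0 | 1.0 |
| 5 | 14.7 | 7.4 | 2.0 | 1.0 |
| 10 | 26.5 | 13.9 | 1.9 | 1.0 |
| 50 | 69.7 | 45.3 | 1.5 | 1.0 |
| 100 | 83.2 | 62.5 | 1.3 | 1.0 |

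Worked line for 10 per 100 patient-years: 0.1/0.3 × (1 − exp(−0.3 × 5.29)) = 26.5%; 0.1/0.7 × (1 − exp(−0.7 × 5.29)) = 13.9%.

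**4. Sensitivity.** These figures use T = 5.31 years, which includes the 7-day residual effect period, and drop-out of 0.1 per year against 0.3, 0.5 and 1.0.
- At 2 events per 100 patient-years the apparent ratios are 1.54, 2.18 and 4.02; at 100 they are 1.18, 1.36 and 1.81.
- With equal drop-out the ratio is 1.00.
- The order can reverse. With 5 events per 100 patient-years in the column with drop-out 0.1, and a rate 1.5 times higher in the column with drop-out 0.5, the crude percentages are 18.3% and 12.4%.

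**5. After the change.** With time at risk counted from the first intake after Week 12, the rate equals L in both columns in every equal-hazard scenario above.

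**The case against.** The best defence is that SAP 6.1 is silent about rates in the other sets but does not exclude them. SAP 7.4.1 and protocol 7.3.4 make the exposure-adjusted rate the primary measure, and SAP section 4 declares no change from the protocol. This stands in part: a reader might infer that the primary analysis, or long-term safety as a whole, rests on crude percentages, and the documents do not support that. But SAP 6.1 is the only text that allocates rates to sets, and it names one. The clock in 7.4.1 does not fit an after-Week-12 period either.

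A reader might also infer that the plan offers no exposure-adjusted comparison of 100 mg with 200 mg. It does, in the dose-at-onset set, and the first 12 weeks are at most 12 of 288 planned weeks (4.2%) for a patient who completes. What is missing is the narrower split by sequence after Week 12.

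Extending the criticism to Part 2 is tempting but fails. That set has one column, and because Part 2 patients are all planned to receive 400 mg from Visit 1 while Part 1 doses stop at 200 mg, the 400 mg dose-at-onset column already gives the rate.

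Nor can one say that 200/200 mg will look worse. The Global Amendment 3 rationale calls 100 mg sub-optimal, which makes earlier departure from 100 mg plausible. However, the remark supports an option to up-titrate, which may keep those patients on drug.

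Finally, rates by sequence have a problem of their own: patients who move from 100 to 200 mg have no sequence column, so 200 mg time could fall under an x/100 label. That objection is sound, and the change has to deal with it.

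**Conclusion.** The point holds in a limited form. For the Part 1 after-Week-12 set, the SAP promises no exposure-adjusted rate by dose sequence, and no other planned analysis supplies one. The reason the SAP gives for adjusting the dose-at-onset set applies here as well.

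The size is hypothetical. It depends on drop-out differing between sequences, on constant hazards, and on event frequency. An apparent ratio near 2 is an illustration for less common events, not a general figure: the distortion shrinks as events become common and vanishes if drop-out is equal. The analysis is descriptive, so no test or error rate is affected. The change is worth making because it is cheap and removes the dependence on time on drug from a table in the main safety analyses.

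**What to change.** In SAP 6.1:

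- For the Part 1 after-Week-12 set, add exposure-adjusted rates with exact 95% confidence intervals and total patient-years, and keep the number and percentage alongside.
- Start time at risk at the first intake after the Week 12 re-assignment. End it at the earliest of first onset or worsening in that period, death, last dose + 7 days, or last contact.
- For patients up-titrated from 100 to 200 mg, split events and time at risk at the date of up-titration and show the later time in a separate column.
- State which sets and columns the SAP 7.4.1 rate covers.
- Correct the reference to a fifth set, and check the set numbers in the neighbouring sentence on exclusions at the same time.

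No addition is needed for the Part 2 set. The cost is SAP wording and a few extra columns from a rate program that is already required; no new data are needed.

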Visit	1 ^{1, 2}	1.1 ³	1.2 ³	1.3 ³	2	2.1 ³	3	4	5	6	7	8	9	10	11	12	13	14
Week	(Day 1)	2	4	8	12	14	24	36	48	60	72	84	96	108	120	132	144	156
Visit window (days)		±7	±7	±7	±7	±3	±7	±7	±7	±7	±7	±7	±7	±7	±7	±7	±7	±7
Informed consent	X																	
Demographics	X																	
Medical history	X																	
Smoking/alcohol history	X																	
Baseline conditions	X																	
In-, ex-criteria	X																	
Concomitant therapy	X	X	X	X	X	X	X	X	X	X	Х	X	Х	X	X	X	X	Х
Body weight	\mathbf{x}^1								X				X				X	
Vital signs	x ¹	X	X	X	X		X	X	X	X	X	X	X	X	X	X	X	X
Physical examination	\mathbf{x}^1	X	X	X	X		X	X	X	X	X	X	X	X	X	X	X	X
Resting 12 lead ECG	\mathbf{x}^1								X				X				X	
Pregnancy testing ⁴	\mathbf{x}^1	X	X	X	X		X	X	X	X	X	X	X	X	X	X	X	X
Adverse Events	X	X	X	X	X	X	X	X	X	X	X	X	X	X	X	X	X	X
Contact IRT	X				X		X	X	X	X	X	X	X	X	X	X	X	X
Dispense study medication	X				X		X	X	X	x	X	X	x	X	X	X	X	X
Collect study medication					X		X	X	X	X	Х	X	Х	X	X	X	X	Х
PASI, sPGA	x ¹				X		X	X	X	X	Х	X	Х	X	X	X	X	Х
																	Ī	

Page 6 of 84

Trial Periods	Screening/ Double Blind Treatment							(Open La	abel Tro	eatment	t						
Visit	1 ^{1, 2}	1.1 ³	1.2 ³	1.3^{3}	2	2.1 ³	3	4	5	6	7	8	9	10	11	12	13	14
Week	(Day 1)	2	4	8	12	14	24	36	48	60	72	84	96	108	120	132	144	156
Visit window (days)		±7	±7	±7	±7	±3	±7	±7	±7	±7	±7	±7	±7	±7	±7	±7	±7	±7
Columbia-Suicide Severity Rating Scale (C-SSRS) ⁷	\mathbf{x}^1				X		X	X	X	X	X	X	х	x	х	X	х	X
Safety laboratory samples	x^2	X	X	X	X		X	X	X	X	X	X	X	X	X	X	X	X
Biomarker samples (serum)	\mathbf{x}^1								X				x					
Whole blood (PBMC) for flow cytometry (pre-dose) 8	\mathbf{x}^1								Х				х					
Termination of trial medication																		
Trial completion 10, 11																		
Vital status collection ¹³																		

Page 7 of 84

Trial Periods					Oper	Label T	[reatme	nt				Follow-Up	
Visit	15	16	17	18	19	20	21	22	23	24	EOT^{12}	EOO ¹¹	
Week	168	180	192	204	216	228	240	252	264	276	288	292	
Visit window (days)	±7	±7	±7	±7	±7	±7	±7	±7	±7	±7	±7	+7	
Informed consent													
Demographics													
Medical history													
Smoking/alcohol history													
Baseline conditions													
In-, ex-criteria													
Concomitant therapy	X	X	X	Х	X	X	X	Х	X	X	х	Х	
Body weight			X				X				X		
Vital signs	X	X	X	Х	X	X	X	Х	X	X	х	Х	
Physical examination	X	X	X	X	X	X	X	X	X	X	X		
Resting 12 lead ECG			X				X				Х		
Pregnancy testing ⁴	X	X	X	X	X	X	X	X	X	X	X	X	
Adverse Events	X	X	X	X	X	X	X	X	X	X	X	X	

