Contact IRT	X	X	Х	X	X	X	X	Х	X	X	Х		
Dispense study medication	X	X	X	Х	X	X	X	Х	X	X			
Collect study medication	X	X	X	Х	X	X	X	Х	X	X	х		
PASI, sPGA	X	X	X	X	X	X	X	X	X	X	X		
Columbia-Suicide Severity Rating Scale (C-SSRS) ⁷	X	x	x	x	x	x	x	x	x	x	x	X	
Safety laboratory samples	X	X	Х	X	X	X	X	X	X	X	X		
Biomarker samples (serum)											Х		
Whole blood (PBMC)													
for flow cytometry											X		
(pre-dose) ⁸													

Page 8 of 84

Trial Periods		Open Label Treatment										Follow-Up
Visit	15	16	17	18	19	20	21	22	23	24	EOT^{12}	\mathbf{EOO}^{11}
Week	168	180	192	204	216	228	240	252	264	276	288	292
Visit window (days)	±7	±7	±7	±7	±7	±7	±7	±7	±7	±7	±7	+7
Termination of trial medication											X	
Trial completion ^{10, 11}												X
Vital status collection ¹³												X

Boehringer Ingelheim 06 Oct 2020

Clinical Trial Protocol Page 9 of 84

Proprietary confidential information © 2020 Boehringer Ingelheim International GmbH or one or more of its affiliated companies

Flow Chart Footnotes:

Visit 1 will occur on the same day as End of Treatment (EOT) Visit in 1407-0030. Weight, vital signs, physical exam, ECG, pregnancy test, PASI, sPGA,

, C-SSRS, biomarker samples, whole blood

(PBMC) for flow cytometry and are performed only once on that day as part of the EOT Visit in 1407-0030. Visit 1 may be delayed up to 16 weeks if necessary for administrative reasons. If Visit 1 is delayed, these procedures will be done at Visit 1, except for PK, Biomarker and flow cytometry samples.

² Safety laboratory samples will be taken twice in the same day as part of both the EOT Visit in 1407-0030 and for Visit 1 in 1407-0005. Visit 1 collection is only for the following laboratory tests that are not assessed at EOT in study 1407-0030: infection testing, glycosylated Hbc, LDL-cholesterol/HDL-cholesterol, cholesterol total, and triglycerides. If Visit 1 is delayed, then a sample will be taken at Visit 1 to include all tests included in the two samples and only one sample will be taken at EOT for 1407-0030.

³For patients entering from Part 1 of trial 1407-0030, Visit 2.1 is a phone visit, with only adverse events and concomitant medication collected. Visits 1.1, 1.2 and 1.3 do not apply. For patients entering from Part 2 of trial 1407-0030, Visits 1.1, 1.2 and 1.3 to be performed at the clinic with all procedures indicated, Visit 2.1 does not apply.

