6.2.2 Treatment period

The treatment period starts with Visit 1 and ends with the EOT visit. The patients will be fasted for each visit.

The patients will return to the clinic for regularly scheduled visits as specified in the Flow Chart. At these visits, the occurrence of safety and efficacy endpoints, trial medication compliance, concomitant therapy or intervention will be assessed.

At all treatment visits, the order of assessments (as applicable) should be followed:

- Completion of the questionnaires
- Physical examination, urine pregnancy, vital signs, and ECG
- Laboratory samples

All assessments must be performed before the medication is taken.

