7.8.2 Laboratory data

The analyses of laboratory data will be descriptive in nature and will be based on BI standards [\(6\)](#). The number and percent of patients with possibly clinically significant on treatment abnormalities as identified by use of clinically significant ranges for each laboratory parameter collected will be presented. The patients from both parts of 1407-0030 with possibly clinically significant abnormalities will be identified by actual treatment received at study entry.

Each laboratory value will be graded using the RCTC (version 2.0) grading of laboratory abnormalities. A summary table of the baseline grade compared with the last available on treatment grade will display the number and percent of each type of transition in grade by laboratory parameter within each treatment period and treatment group. A second table will show the number and percent of patients with each type of transition from baseline to their worst on-treatment grade.

A graphical summary highlighting potential cases of Hy's Law by actual treatment received at study entry will be presented. The maximum on-treatment values of total bilirubin and ALT will be plotted each on a scale as multiples of the upper limit of normal. The figure will show areas that meet the criteria of cholestasis (total bilirubin $> 2 \times$ ULN), Temple's corollary (ALT $> 3 \times$ ULN) and Hy's Law as the combination of these two factors. A similar figure using maximum AST values in place of ALT will be constructed. An accompanying listing will show by sample date and study day the full course of the total bilirubin, ALT, AST and alkaline phosphatase values for patients whose total bilirubin are $> 2 \times$ ULN or AST or ALT values $> 3 \times$ ULN at any time during the study (all treatment periods). The listing will indicate where the value meets the criteria, either falling in the cholestasis range, that for Temple's corollary or where the combination meets that for Hy's Law itself.

Laboratory measurements taken up to the residual effect period of 7 days after the last administration of study drug will be considered as on-treatment.

Study visits will be presented by the Visit labels in [Table 6.7:1](#).

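### First-12-week laboratory tables of any abnormality and worst grade set up to four scheduled samples per patient at 400 mg against one at the lower doses

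*SAP*

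**What the plan says.** **Sampling.** The protocol Flow Chart schedules safety laboratory samples at Visits 1, 1.1, 1.2, 1.3 and 2, that is Day 1 and Weeks 2, 4, 8 and 12: "Safety laboratory samples x^2 X X X X". Footnote 3 divides these visits by part. For Part 1, "Visits 1.1, 1.2 and 1.3 do not apply". For Part 2, "For patients entering from Part 2 of trial 1407-0030, Visits 1.1, 1.2 and 1.3 to be performed at the clinic with all procedures indicated". Protocol 6.2.2 adds: "All assessments must be performed before the medication is taken". So the Visit 1 sample is not on treatment in this trial, and the Part 1 Week 12 sample precedes the open-label dose and belongs to the first 12 weeks.

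**Summaries.** For laboratory data, vital signs and suicidal ideation, SAP 6.1 says that "summaries will be presented for the entire study, for the first 12 weeks of the study and after 12 weeks on study", and then: "For these outputs data from patients who rolled over from Part 1 and Part 2 of study 1407-0030 will be combined".

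**Statistics.** SAP 7.8.2 plans three relevant laboratory tables:
- patients with a possibly clinically significant on-treatment abnormality, with both parts shown by treatment at study entry;
- baseline grade against the last available on-treatment grade, shown for each group and period;
- a worst-grade shift table, described thus: "A second table will show the number and percent of patients with each type of transition from baseline to their worst on-treatment grade".

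Protocol 7.3.4 intends a descriptive comparison of treatment groups on the percentage of patients with abnormal laboratory values.

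**The concern.** Two of the three tables record an extreme: whether any sample was abnormal, and the worst grade reached. Both can only rise as samples are added. If the groups are sampled at different rates within the period shown, the percentages differ for that reason alone.

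Here the more heavily sampled group is 400 mg, which protocol 3.1 calls the anticipated therapeutic dose. The artefact points towards more laboratory abnormality at the highest dose. A reader could take it for a dose-related signal, or could put a real signal down to sampling. Long-term safety information for registration is a stated purpose of the trial.

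Nothing in the SAP corrects for this. The rule in SAP 6.7 for choosing among several values in one window covers efficacy endpoints only, and no adjustment for the number of laboratory samples is given.

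**Working it through.** The documents state no figure on this point, so there is none to reproduce.

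**Step 1: scheduled on-treatment laboratory samples per patient** (Flow Chart and footnote 3, full follow-up).

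| Period | Part 1 (placebo to 200 mg) | Part 2 (400 mg) |
|---|---|---|
| First 12 weeks | 1 (Week 12) | 4 (Weeks 2, 4, 8, 12) |
| After Week 12, to Week 288 | 23 | 23 |
| Entire study | 1 + 23 = 24 | 4 + 23 = 27 |

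**Step 2: chance that a patient has at least one abnormal sample, with no drug effect.** Let p be the probability that one sample is abnormal, equal at every dose, and k the number of samples. If samples are independent:

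P(any) = 1 − (1 − p)^k

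For p = 5% and k = 4: 1 − 0.95^4 = 18.5%, against 5.0% for k = 1.

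Repeat samples in one patient are correlated. With an exchangeable normal model and latent correlation ρ, and c the standard normal quantile at 1 − p:

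P(any) = 1 − ∫ φ(u) · Φ((c − √ρ·u) / √(1 − ρ))^k du

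**Step 3: results for k = 4 against k = 1.** The rates p and correlations ρ are assumptions; the documents give neither.

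| One sample (p) | ρ = 0 | ρ = 0.3 | ρ = 0.6 | ρ = 0.9 |
|---|---|---|---|---|
| 2% | 7.8% (ratio 3.9) | 7.1% (3.6) | 5.9% (2.9) | 3.8% (1.9) |
| 5% | 18.5% (3.7) | 16.4% (3.3) | 13.3% (2.7) | 8.8% (1.8) |
| 10% | 34.4% (3.4) | 29.5% (3.0) | 23.9% (2.4) | 16.3% (1.6) |

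The ratio reaches 1 only as ρ approaches 1. With the approximately 90 patients planned for Part 2 and p = 5%, the table would be expected to flag 90 × 0.133 = 12.0 patients at ρ = 0.6, against 90 × 0.05 = 4.5 on one sample each.

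**Step 4: whole-study tables.** With k = 27 against k = 24 and the same p and ρ, the ratio is about 1.02 to 1.09. The three extra samples matter little there.

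**Step 5: after the change proposed below.** With one sample per patient in each group, the expected percentage is p in every column and the ratio is 1.0.

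**The case against.** **Are the two tables split at Week 12 at all?** SAP 7.8.2 mentions treatment periods only for the last-available-grade table, which uses one value per patient and is not inflated. The worst-grade and any-abnormality tables carry no period of their own, and the note to SAP Table 6.1: 1 divides on-treatment time at Week 12 only for Part 1. The split therefore rests on the general sentence in SAP 6.1. That sentence covers laboratory data without exception, so the reading is the natural one, but it is an inference. If both tables were whole-study only, the effect would be small (Step 4).

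**Vital signs.** A reader might infer the same defect, because they too are sampled four times against once: "Vital signs x ¹ X X X X". The documents do not support this. SAP 7.8.3 plans only descriptive statistics and names no worst value or abnormality count.

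**Scope within the laboratory panel.** HbA1c, lipids and infection tests are drawn only at Visits 1, 5, 9, 13, 17, 21 and EOT (protocol Table 5.2.3: 1), so they are unaffected. Unscheduled retests are allowed (protocol 6.1), so one and four are scheduled counts.

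**Other differences between the parts.** They also differ in fed or fasted dosing, length of prior treatment, entry criteria and a possible gap before Visit 1, and there is no randomisation. Equal sample counts would not make this a clean dose comparison. That stands, but unequal sampling is the one difference that the analysis can remove.

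**Descriptive aim.** No hypothesis is tested, the DMC reviews accumulating safety data, some displays put each treatment on its own page, and the primary endpoint is untouched. This limits the consequence. It does not remove it, because the descriptive percentages are themselves what is distorted.

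**Conclusion.** The point holds for two laboratory displays: the first-12-week versions of the any-abnormality table and the worst-grade shift table. The sample counts come directly from the Flow Chart. The period split comes from reading SAP 6.1 with SAP 7.8.2. Under the assumed 2% to 10% abnormal per sample, the expected ratio with no drug effect is about 2.4 to 3.9 for latent correlations of 0 to 0.6, and 1.6 to 1.9 at 0.9. The direction is firm for any correlation below 1; the size is not known from the documents.

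A reader might go further and say that 400 mg will show an excess. That is only an expectation, and its size depends on rates and correlations not given. Nor are all first-12-week safety tables affected.

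The SAP already accepts the principle. For adverse events it separates the two parts, does not split Part 2 at Week 12, and adds exposure-adjusted rates where time on dose varies. The change should be made, but it does not bear on the primary analysis.

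**What to change.** In SAP 6.1 and 7.8.2, for the first-12-week any-abnormality and worst-grade laboratory tables:

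1. Base the between-dose columns on one value per patient that both parts share: the nominal Visit 2/Week 12 sample or, for patients who stop earlier, the EOT sample if it meets the on-treatment definition.
2. State that this is not every value in the Week 12 window of SAP Table 6.7: 1. That window runs from Day 2 to Day 125, so the Week 2, 4 and 8 samples could otherwise re-enter through it.
3. Show the all-sample results (Weeks 2, 4, 8 and 12) for 400 mg in a separate Part 2 table that states the number of samples per patient.
4. Say explicitly which laboratory tables are split at Week 12.

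The cost is SAP wording and one extra table. The between-dose column uses fewer 400 mg samples, but no 400 mg data are lost and no visit or procedure changes. A cheaper alternative is to keep all samples in the combined tables and print the number per patient. That discloses the imbalance without removing it.
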